Based on our preliminary work, our research group obtained funding from the Laerdal Foundation to conduct an internal pilot trial of the DOSE VF protocol (<https://clinicaltrials.gov/ct2/show/NCT03249948>) previously approved by the Sunnybrook Health Sciences Center REB. The pilot trial was designed to determine the feasibility of conducting a full-scale randomized trial in this population.^{17,18} The pilot RCT completed on September 9, 2019, trained over 2,500 paramedics in the technique of DSED and vector change defibrillation (VC). The pilot took place in four paramedic services in Ontario (Toronto, Peel, Halton and Simcoe) with all services actively enrolling patients. All paramedics received in-person training using a combination of didactic, video and simulated scenarios prior to the study launch. All eligible patients with refractory VF (n=152) in the participating paramedic services have had paramedics successfully apply both VC and DSED. The DOSE-VF Pilot RCT demonstrated that the protocol is feasible with 89.5% of patients receiving the treatment they were randomized to and 90.2% of patients receiving an intervention shock prior to shock 6 in the resuscitation. As well, no safety concerns were noted (no reports of defibrillator damage, skin burns, inadvertent shocking of paramedics or bystanders) and was well accepted by paramedics in the field. We have as well been able to determine the number of cases occurring in each service during the pilot RCT (varying from 1.4-6.1 cases/month) allowing us to accurately calculate the number of patients required to perform an adequately powered definitive RCT. Finally, we observed that the rate of VF termination and ROSC were greater in both

interventions then standard defibrillation. Specifically, in the standard group, 66.6% of cases resulted in VF termination, compared to 82.0% in VC and 76.3% in the DSED group. ROSC was achieved in 25.0%, 39.3% and 40.0% of standard, VC and DSED groups, respectively. The DOSE-VF pilot RCT has established the feasibility of proceeding with a definitive, adequately powered RCT to determine whether employing a standardized approach to alternative defibrillation strategies early in the treatment of refractory VF may impact clinical outcomes.

Objective: The objective of this study is to compare two novel therapeutic defibrillation strategies (DSED and VC) against standard practice for patients remaining in refractory VF during out-of-hospital cardiac arrest.

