In response to the need for more efficient trial designs that accelerate discovery and minimize costs, it has been recommended that researchers consider employing multi-arm trials designed for logistical efficiency.²¹ In a multi-arm trial, several treatments are simultaneously assessed against a common control group within a single randomized trial, allowing sizeable gains in efficiency. Relative to conducting separate trials for each experimental treatment, a multi-arm design has been shown to require a lower total sample size and financial resources than separate, sequential two-arm trials.²²

From our internal pilot trial discussed earlier, we observed that across our paramedic services, the annual prevalence of paramedic treated out-of-hospital cardiac arrest for these regions is approximately 4,000; of which 800 (20.0%) patients will present in VF. Our pilot data suggests that approximately 180 patients per year meet the study criteria for refractory VF. Holmen et al.²⁴ demonstrated a 30 day survival rate of 28.7% for patients receiving 1-3 shocks, declining to 12.4% for those receiving 4-10 shocks, and 4.9% for those receiving greater than 10 shocks. Based on these findings, we assumed a baseline survival rate of 12% for patients who will meet our study criteria. This baseline survival rate will be confirmed by comparing to the baseline survival rate of the standard defibrillation arm of the pilot RCT and will be adjusted according to this value.

We hypothesize that DSED and VC defibrillation earlier in the resuscitation will result in survival as high (or higher) as standard defibrillation. We project a minimum absolute increase of 8% in survival to hospital discharge when VC or DSED strategies are employed as per our protocol, compared to standard care.

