Using these baseline estimates, and assuming a fixed number of paramedic service clusters ($n=6$), we will enroll approximately 20-70 patients per cluster over one year. Data from the internal pilot RCT will be included in the final analysis.¹⁷ The study design assumes that each cluster will cross over twice to receive each of three treatment approaches (standard defibrillation, DSED and VC) for approximately six months. We assumed a plausible intra-cluster correlation (ρ) of 0.010 and a plausible inter-period correlation (η) of between 0.008 and 0.010 and without multiplicity correction, as has been recommended for exploratory trials involving multiple treatment arms.^{22,25} Under these conditions, the trial will have adequate power (>80%) with an α level 5%, to detect a minimally important 8% absolute difference in survival to hospital discharge with a sample size of 310 patients per arm (total sample size of 930 patients; approximately 150 patients from internal pilot RCT and 780 patients from the definitive RCT).

Statistical Analysis and Mock Tables (**Appendix 3**):

For this three-arm trial, two treatment strategies (DSED and VC) share a common control arm (standard defibrillation). This approach is chosen to maximize efficiency, allowing comparison of two new treatments to usual care in a single three-armed trial. The primary analysis will compare DSED to standard defibrillation and VC defibrillation to standard defibrillation. A secondary analysis will compare DSED to VC defibrillation. We hypothesize

that resuscitation involving DSED and resuscitation involving VC defibrillation will have superior outcomes compared to resuscitation using standard defibrillation. Because this trial is focused on answering the efficacy question for each treatment strategy separately, and the interpretation of the results of one comparison have no direct bearing on the interpretation of the other. In this situation, no multiplicity adjustment is required.^{22, 25, 26}

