All tests will be 2-sided with $p < 0.05$ denoting statistical significance. The unit of analysis for the comparisons will be the individual patient. All patients will be analyzed according to randomized treatment assignment (intention-to-treat analysis). Based on the DOSE VF pilot RCT secondary analyses will be performed based on actual treatment received, appropriate randomization performed, and appropriate randomization performed with optimal intervention shock timing (shock 4). We will also perform an a priori subgroup analysis comparing rates of survival to hospital discharge for those randomized to DSED who receive DSED after three failed successive standard shocks (early DSED or first DSED shock is shock 4-6) to those who receive DSED after six failed successive standard shocks (late DSED or first DSED shock is shock 7 or later). Last, we will perform a sensitivity analysis to examine the impact of trial phase (pilot study, pre-COVID, and during COVID) on our outcomes. The binary primary outcome, survival to hospital discharge, will be compared across the arms of DSED and VC defibrillation as an adjusted odds ratio with 95% confidence intervals (CIs) using the standard arm as the reference group.²⁷ We will use a generalized linear mixed model (GLMM; logit link) with random effects for cluster-period effect, and using fixed-effects for cluster and for the period, to account for the effect of period on the outcome, as has been recommended for the analysis of cluster crossover trials.^{28,29} The primary analysis will also adjust for the following baseline variables known to impact outcomes after out-of-hospital cardiac arrest: age, sex,

bystander witnessed arrest, bystander CPR provided, time to first arrival, public versus private location, epinephrine and antiarrhythmic use.³⁰ We will also test for effect modification by trial phase, comparing effectiveness in the internal pilot trial and the larger definitive trial. Odds ratios with 95% CIs for secondary outcomes will be calculated in a similar manner, where appropriate.

Consent Waiver

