On Friday January 28th 2022, the DSMB met virtually via Zoom to discuss the current status of the DOSE-VF RCT. Prior to the meeting, [name] circulated a summary report detailing the current status of the DOSE-VF trial, which was reviewed by DSMB members [name], [name], and [name]. Steering committee members [name], [name], and [name] also attended the DSMB meeting to provide context and input regarding current challenges. This letter is intended to summarize the discussion from the DSMB meeting.

After a long pause due to the COVID-19 global pandemic, five sites restarted enrolment in September 2020. The sixth site, Toronto Paramedic Service, began enrolling patients again in October 2021 (after a 19-month hiatus). Since restarting the trial, 132 patients have been enrolled, bringing the total study enrolment to 379 with good balance between all arms (DSED 122; Standard 128; Vector Change 129 patients). Despite the continued enrolment of patients, [name] presented some concerns regarding the ability of paramedics to continue to enrol patients in the study due to the challenges presented by the ongoing COVID-19 pandemic. Some of the major concerns relate to paramedic protocol compliance during COVID-19; paramedic staffing concerns and service response times; and the reported worldwide decrease in overall survival from cardiac arrest (primary outcome of the study) during COVID-19.

[name] reported an overall decrease in randomization compliance during COVID-19 from 92% (pre-COVID) to 83% (during COVID), with compliance dropping in both intervention arms to 73% (down from 83% for vector change and 92% for DSED prior to the pandemic) with no significant drop in standard arm compliance. This is concerning as it has the potential to bias the trial results towards the null effect. The investigators have followed up with letters, video refreshers, sign postage at all stations and other methods in an attempt to keep compliance high, but feedback from paramedic services suggests compliance is difficult due to reduced staffing, increased response times, and competing priorities associated with COVID-19 protocols on scene and cardiac arrest treatment.

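### The 8-point effect projected for per-protocol use is carried undiluted into the power for an intention-to-treat comparison, although the pilot showed 89.5% adherence; on the direct reading, power is about 69%, not above 80%

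*Combined protocol and SAP*

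**What the plan says.** - **Effect (Sample Size).** "We project a minimum absolute increase of 8% in survival to hospital discharge when VC or DSED strategies are employed as per our protocol". The comparator is the standard arm. The control rate is given as: "we assumed a baseline survival rate of 12% for patients who will meet our study criteria".
- **Power (Sample Size).** The stated aim is "to detect a minimally important 8% absolute difference in survival to hospital discharge with a sample size of 310 patients per arm". For this aim the section claims power above 80% at an alpha of 5%. The listed inputs are six clusters, an intra-cluster correlation of 0.010, an inter-period correlation of 0.008 to 0.010, no multiplicity correction, the 12% baseline and the 8 points. Adherence is not among them.
- **Analysis (Statistical Analysis and Mock Tables).** "All patients will be analyzed according to randomized treatment assignment (intention-to-treat analysis". Analyses by treatment received and by appropriate randomization are secondary. On testing: "All tests will be 2-sided with $p < 0.05$ denoting statistical significance".
- **Adherence (The DOSE-VF Pilot RCT).** The pilot found "89.5% of patients receiving the treatment they were randomized to", with no breakdown by arm. About 150 pilot patients count towards the 930.
- **Fallback (Study Protocol, Strategy 3).** When no second defibrillator is at hand, a patient in the DSED arm receives standard shocks until one can be obtained.
- **Later information (DSMB letter, January 28, 2022).** Compliance fell to 73% in both intervention arms during the pandemic, "down from 83% for vector change and 92% for DSED prior to the pandemic". The protocol is version 6.2 of June 11 2021, so the letter came after it.

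**The concern.** An effect projected for patients treated as the protocol prescribes is not the difference between arms as assigned, unless everyone adheres. Patients who stay in an intervention arm without receiving the intervention pull that arm's survival towards the control rate. The plan itself separates assignment from treatment received, since it analyses both. Yet one figure of 8 points serves as the projected per-protocol effect and as the difference for the intention-to-treat power.

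What is at stake is the meaning of the stated power. If 8 points is the per-protocol effect, the power above 80% does not describe the primary analysis. This matters more because the DSMB letter worries about bias towards the null from falling compliance and suggests moving the primary population from intention-to-treat to per-protocol. A reader weighing either analysis needs to know which one the 8 points was meant for.

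**Working it through.** **Inputs.** Control survival 12%, difference 8 points, 310 per arm, two-sided 5%, intra-cluster correlation ρ = 0.010 and inter-period correlation η = 0.008 to 0.010 (Sample Size; Statistical Analysis). Six services each apply each arm twice, giving 12 cluster-periods per arm and m = 310/12 = 25.8 patients per cluster-period. Adherence is 89.5% (pilot section).

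**Formulas.** Power = Φ{[Δ√n − 1.96√(2p̄(1−p̄))] / √(p₁(1−p₁) + p₂(1−p₂))}, with p̄ the mean of p₁ and p₂ and n divided by the design effect. The cluster-crossover design effect is 1 + (m−1)ρ − mη. It equals 0.990 at η = 0.010 and 1.042 at η = 0.008.

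**Step 1: the plan's own figure.** For 12% v 20% with design effect 1:
- (0.08 × √310 − 1.96 × √(2 × 0.16 × 0.84)) / √(0.1056 + 0.1600) = (1.4085 − 1.0162) / 0.5154 = 0.761, so power is 77.7%.
- Over the η range it is 76.0% to 78.1%. 80% power needs 329 per arm (326 to 343).
- Unpooled and arcsine versions with design effect 1 give about 78% at 310. No two-sided version tried exceeds 80%.

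There is thus a small shortfall at a full 8 points, separate from adherence.

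**Step 2: dilution at the pilot's adherence.** Assume that non-adherent intervention patients have control survival and that the standard arm is uncontaminated.
- Intention-to-treat difference = 0.895 × 8 = 7.16 points, so 12% v 19.16%.
- (0.0716 × √310 − 1.0053) / 0.5104 = (1.2606 − 1.0053) / 0.5104 = 0.500, so power is 69.2%.
- Over the η range it is 67.4% to 69.6%. For scale, 80% power at this difference needs about 402 per arm.

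**Step 3: dilution alone.** Start from an exact 80%, where the standardised effect is 1.96 + 0.8416 = 2.8016. Then Φ(2.8016 × 0.895 − 1.96) = Φ(0.547) = 70.8%. Adherence by itself costs about 9 points of power.

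**Step 4: partial benefit.** If non-adherent patients keep half the benefit, the factor is 0.895 + 0.105/2 = 0.9475. The difference is 7.58 points and power is 73.6%.

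**Step 5: sensitivity, using later information.** The arm-level pre-pandemic figures come from the DSMB letter and post-date version 6.2.

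| Adherence | ITT difference | Power at 310 (η range) | From an exact 80% |
|---|---|---|---|
| 100% | 8.00 | 77.7% (76.0–78.1) | 80% |
| 92% (DSED, letter) | 7.36 | 71.3% (69.6–71.8) | 73% |
| 89.5% (pilot, all arms) | 7.16 | 69.2% (67.4–69.6) | 71% |
| 83% (VC, letter) | 6.64 | 63.2% (61.4–63.6) | 64% |

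The 89.5% is pooled over arms. If the standard arm were fully adherent and the arms equal in size (assumptions), the intervention arms would average (3 × 0.895 − 1)/2 = 84%. That gives 6.7 points and 64% power.

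**Step 6: the other reading.** If 8 points is the intention-to-treat difference, the effect needed in treated patients is 8/0.895 = 8.9 points. At 92% and 83% adherence it is 8.7 and 9.6 points.

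**The case against.** The strongest reply is that no mismatch is proven. The power sentence calls the 8 points minimally important, and a minimally important difference is naturally a target for the contrast analysed, which needs no dilution. The qualifier in the projection could mean planned early use, as against the late ad hoc use described in the Background. It could also include the permitted fallback to standard shocks, so that a DSED patient who falls back is still treated per protocol. This stands as far as it goes: a reader might infer that the trial was demonstrably sized on an effect its primary analysis will not estimate, and the text does not establish that. It does not dispose of the point. The fallback concerns DSED only and cannot explain non-adherence under VC. If intention-to-treat was meant, the larger effect required in treated patients is nowhere stated.

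A reader might also infer that adherence of 83–92% was known when 310 per arm was set. The documents do not support this. Those arm-level figures appear only in the January 2022 letter; the protocol's own figure is the pooled 89.5%.

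Third, zero benefit in non-adherent patients is an assumption. The documents do not say what those patients received, and late or partial intervention shocks may have helped. The half-benefit case shows a smaller loss, though power still falls below 80%.

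Finally, the 69%, 71% and 63% at 310 per arm should not be read as the cost of dilution alone. They start from 77.7%, so they include the separate shortfall at a full 8 points.

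**Conclusion.** The point holds in a limited form. The plan projects 8 points for use as the protocol prescribes, puts the same 8 points into the power for an intention-to-treat comparison, and makes no allowance for adherence although it reports 89.5% in the pilot. On that reading, with no benefit in non-adherent patients and an uncontaminated standard arm, power at 310 per arm is about 69% (67–70%). That compares with about 78% (76–78%) at a full 8 points and the stated figure above 80%. Half benefit gives about 74%. Because 8 points may have been meant as the intention-to-treat target, the defect is an unstated definition whose more direct reading overstates the power, and not a demonstrated error of calculation.

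**What to change.** In Sample Size, say whether 8 points is the difference under per-protocol use or the intention-to-treat difference.

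- **If per-protocol use:** restate the power for the primary analysis. For example: *With 89.5% adherence as in the pilot, and assuming no benefit in non-adherent patients and no contamination of the standard arm, 8 points is an intention-to-treat difference of about 7.2 points. Power at 310 per arm is about 69% (67–70% over the stated inter-period correlations), or about 74% if non-adherent patients keep half the benefit.* Report the loss from dilution (an exact 80% to about 71%) separately from the shortfall at a full 8 points (about 78%). The letter's pre-pandemic figures (DSED 92%, VC 83%: about 71% and 63%) may be added only as a sensitivity range, labelled as later information.
- **If intention-to-treat:** say so, and state the treated-patient effect it implies: about 8.9 points at 89.5% adherence, and 8.7 to 9.6 points at 92% to 83%.

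Either version takes a few sentences and needs no extra patients. The cost is a less favourable stated power, or a more demanding stated effect in treated patients.

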This will be a three-arm, cluster randomized trial with crossover conducted in six regions of Ontario, Canada (Peel, Halton, Toronto, Simcoe, London and Ottawa). These six regions were

selected because each has its own paramedic service, and all have previously participated in and successfully completed prehospital resuscitation trials.^{19,20} Two treatment strategies (DSED and VC) will be simultaneously assessed against a common control group (standard defibrillation). This approach has been chosen to maximize efficiency, allowing comparison of two new treatments to usual care in a single three-armed randomized trial.^{21,22}

The clusters will be defined by the paramedic service in each of the six regions and each cluster will crossover at least twice per year to receive one of three treatment approaches (standard care, DSED or VC) for six months. Each service will apply each of the three treatment arms twice over the duration of the study. The annual prevalence of paramedic treated out-of-hospital cardiac arrest for these regions is approximately 4,000; of which 800 (20.0%) patients will present in VF. Our pilot trial suggests that approximately 180 patients per year will meet the study criteria for refractory VF. The study protocol will be approved by each local institutional Research Ethics Board and is registered with clinicaltrials.gov. (<https://clinicaltrials.gov/ct2/show/NCT04080986>).

All adult (≥ 18 years) patients remaining in refractory VF or pVT during out-of-hospital cardiac arrest of presumed cardiac etiology will be eligible for inclusion. Patients suffering a traumatic cardiac arrest, patients with pre-existing do not resuscitate orders and patients in recurrent ventricular fibrillation (defined as secondary presentation of VF or those presenting in VF but did not receive three consecutive defibrillation attempts) will be excluded. Patient's whose initial care was provided by non-participating EMS agencies or fire services will be excluded.

Study Protocol:

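### The power of more than 80% claimed for 310 patients per arm does not follow from the printed inputs, which give about 76% to 78.5% per comparison

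*Combined protocol and SAP*

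**What the plan says.** The Sample Size section sets the control rate: "we assumed a baseline survival rate of 12% for patients who will meet our study criteria". It projects an absolute gain of at least 8 points for either new strategy. It also says that the 12% will be compared with survival in the pilot's standard arm and "will be adjusted according to this value", but no adjusted rate appears anywhere in the document.

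For clustering, the section takes six paramedic services, states that "we will enroll approximately 20-70 patients per cluster over one year", and assumes an "intra-cluster correlation (ρ) of 0.010 and a plausible inter-period correlation (η) of between 0.008 and 0.010". The calculation is made "without multiplicity correction, as has been recommended for exploratory trials involving multiple treatment arms". On that basis it concludes that "the trial will have adequate power (>80%) with an α level 5%, to detect a minimally important 8% absolute difference" in survival to discharge "with a sample size of 310 patients per arm", or 930 in total. No formula, software or design effect is named.

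Three other statements fix the calculation. Study Design and Population says: "Each service will apply each of the three treatment arms twice over the duration of the study". The Statistical Analysis section makes all tests two-sided at 0.05. It also defines the primary analysis as two separate comparisons, each new strategy against standard defibrillation.

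**The concern.** The power sentence is presented as the result of the inputs printed around it, and those inputs are complete enough to check. They give less than 80%, even when clustering is ignored. The sentence is the plan's justification for 310 per arm, so funders, ethics boards and readers of the final report would take from it a planned power that the stated assumptions do not deliver.

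The interim sample-size review does not close the gap. The Data and Safety Monitoring Board section links an increase to event rates below expectation, whereas this shortfall is present when the 12% assumption is exactly right.

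**Working it through.** **Inputs.** Control rate 0.12 and difference 0.08, so 0.12 versus 0.20 (Sample Size). n = 310 per arm, ρ = 0.010, η = 0.008 to 0.010, α = 5%, no multiplicity correction (Sample Size). Two-sided tests and pairwise comparisons with standard (Statistical Analysis). Six services each apply each arm twice (Study Design and Population), giving 12 cluster-periods per arm, 36 in all, and a mean size m = 930/36 = 25.8.

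**Step 1: no clustering.**

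- Unpooled variance: SE = √[(0.12×0.88 + 0.20×0.80)/310] = √(0.2656/310) = 0.02927. Then 0.08/0.02927 = 2.733, and power = Φ(2.733 − 1.960) = Φ(0.773) = 78.0%.
- Pooled variance under the null: SE₀ = √(2×0.16×0.84/310) = 0.02945. Power = Φ[(0.08 − 1.960×0.02945)/0.02927] = Φ(0.761) = 77.7%.
- Arcsine: h = 2·arcsin√0.20 − 2·arcsin√0.12 = 0.2198. Power = Φ(0.2198×√155 − 1.960) = Φ(0.777) = 78.1%.
- Log odds ratio: ln(0.2500/0.1364) = 0.606, with SE = √[(1/0.1056 + 1/0.16)/310] = 0.2252. Power = Φ(2.692 − 1.960) = 76.8%.
- Exact binomial enumeration of the z test: 78.2%.

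None reaches 80%.

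**Step 2: clustering.** The plan gives no formula. I assume the standard cluster-crossover design effect, DE = 1 + (m − 1)ρ − mη, and replace n by 310/DE.

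| η | DE (m = 25.8) | Effective n per arm | Unpooled | Pooled | Arcsine | Log OR |
|---|---|---|---|---|---|---|
| 0.010 | 0.990 | 313.1 | 78.4% | 78.1% | 78.5% | 77.2% |
| 0.009 | 1.016 | 305.2 | 77.4% | 77.0% | 77.5% | 76.1% |
| 0.008 | 1.042 | 297.6 | 76.4% | 76.0% | 76.5% | 75.1% |

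The three risk-difference formulas therefore span 76.0% to 78.5%. The log-odds-ratio column is shown because the planned model reports an odds ratio; it is lower throughout.

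**Step 3: does the period size matter?** The plan's 20 to 70 patients per cluster per year means 10 to 35 per six-month period. When η = ρ = 0.010, DE is 0.990 whatever m is, so no choice of m lifts power above 78.5%. At η = 0.008, m = 10 gives DE 1.010 and 77.3% to 77.7%, and m = 35 gives DE 1.060 and 75.3% to 75.7%.

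**Step 4: what would give 80%?** Ranges cover the unpooled, pooled and arcsine formulas.

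| Quantity | η = 0.010 | η = 0.008 |
|---|---|---|
| n per arm for 12% versus 20% (m = n/12) | 322 to 326 | 341 to 345 |
| Difference from 12% detectable with 310 per arm | 8.2 points | 8.4 to 8.5 points |
| Highest baseline at which +8 points has 80% power | 11.1% to 11.3% | 10.2% to 10.4% |

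The required size exceeds 310 by 12 to 35 patients per arm (12/310 = 4%, 35/310 = 11%). On the log-odds-ratio formula it is 333 and 353.

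**The case against.** The strongest reply is that Step 1 does not describe the planned analysis. The primary model adjusts for age, sex, witnessed arrest, bystander CPR and other prognostic variables, and in a logistic model such adjustment raises power. A simulation of 12% versus 20% with 310 per arm and no clustering gave adjusted power of about 78%, 81% and 83% when the covariates' combined AUC was 0.64, 0.70 and 0.75. The adjusted analysis may therefore reach 80%. That stands as a possibility, and for that reason the finding is confined to the printed inputs. It does not reproduce the plan's figure: the AUCs are assumed, the documents give none, and the Sample Size section does not say that any gain from adjustment was counted.

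A second reply is that 12% was provisional. By version 6.2 (June 2021) the pilot, completed in September 2019, could have supplied another rate. A 10% baseline gives 80.5% to 83.0% across the η range. An 11% baseline is enough only at η = 0.010 (80.2% to 80.7%) and falls short at η = 0.008 (78.2% to 78.7%). If a lower rate was used, it is not printed, and printing it is one of the two remedies below.

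Other calculations can exceed 80%, but they are not the ones planned. One-sided 5% testing gives 86.0% (pooled, unclustered) but contradicts the two-sided rule. The chance that at least one of the two comparisons succeeds is about 90%, and an omnibus test of three arms gives about 80.4% without clustering; neither is the separate pairwise question that the plan poses.

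Finally, the gap is small, and enrolment stood at 379 when the monitoring board recommended stopping at all sites but one. Both points are true and limit the practical consequence. They do not make the planned-power statement correct.

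**Conclusion.** The concern holds. On 12% versus 20%, two-sided 5% and 310 per arm, no unadjusted pairwise calculation reaches 80%. The unclustered shortfall of about 2 points needs no assumption about clustering. With the assumed design effect, the claim is too high by at least 1.5 to 2 points at η = 0.010 and by 3.5 to 4 points at η = 0.008. The clustered figures rest on that design effect and on equal cluster-periods of about 26 patients. All the figures rest on 12% being the baseline actually used and on no credit for covariate adjustment. The finding concerns the planned-power statement only, not the early stop.

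**What to change.** In the Sample Size section, name the formula or software and the final baseline rate behind the power statement. Then take one of two routes.

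- If 12% stands, replace the claim with the recomputed figure: about 76% to 78.5% power per comparison at 310 per arm, for ρ = 0.010 and η from 0.008 to 0.010. An equivalent statement is that 310 per arm has 80% power for a difference of about 8.2 to 8.5 points.
- If a pilot-adjusted baseline, a simulation or an allowance for covariate adjustment was used, print it with its assumptions and show the resulting power across the whole η range.

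The cost is one reworded sentence and a slightly less favourable stated power. No extra enrolment is needed.
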